8.3. Analysis Methods

8.3.1. Primary Efficacy Analyses

The primary endpoint is the proportion of subjects who experience worsening of asthma by Week 24 as defined by at least one of the following:

- On 2 consecutive days, AM PEF \leq 75% of mean AM PEF measured over the last 7 days of the Run-in
- $FEV_1 < 80\%$ of baseline (Visit 2)
- Increase in rescue medication use of ≥ 6 puffs/day on 2 consecutive days compared to mean use over the last 7 days of the Run-in
- Increase in ACQ-5 score of ≥ 0.5 compared to baseline (Visit 2)
- The occurrence of a severe asthma exacerbation (asthma attack) defined as deterioration of asthma that leads to the use of systemic corticosteroids for at least 3 days, hospitalization, or an Emergency Department visit

Logistic regression modeling will be used to compare each GB001 group with placebo. The model will include covariates for treatment group, ICS dose (medium or high) at randomization, region (North America, Eastern Europe, Western Europe), baseline pre-bronchodilator FEV₁, and baseline ACQ-5 score. If the full model does not converge, a model with treatment group, ICS dose at randomization, and region as covariates will be utilized. If this reduced model does not converge, a model with treatment group and ICS dose at randomization will be used. In the rare case that convergence issues remain, only treatment group will be included in the model.

The number and proportion of subjects meeting the primary endpoint and corresponding 95% Wilson (Score) CIs (Wilson, 1927) will be summarized by treatment group. ORs, corresponding asymptotic 95% CIs along with the absolute differences and corresponding 95% CIs, and p-values will be summarized for each GB001 group versus placebo. The 95% CIs for the absolute difference will be Newcombe continuity-corrected CIs (Newcombe, 1998). Percentage reductions and corresponding 95% CIs will also be summarized. Lastly, the number and proportion of subjects meeting each component of the primary endpoint, with observed worsening of asthma, and with an assigned status of asthma worsening will also be summarized by treatment group. Subjects can meet more than one component of the primary endpoint.

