8.3.1.1.4. Sensitivity Analysis #4: Multiple Imputation

If the number of subjects overall with a missing observed status for asthma worsening by Week 24 is \geq 5%, then the following MI approach will be conducted as a sensitivity analysis.

The dichotomous outcome of asthma worsening by Week 24 will be imputed for subjects who have withdrawn from study without having experienced asthma worsening using a MI approach assuming that these subjects with a missing dichotomous outcome would have similar outcomes to subjects who had an observed status of asthma worsening by Week 24. The dichotomous outcome will be imputed directly as opposed to imputing the individual components of the primary endpoint and then deriving the composite outcome.

The following steps will be performed:

- Intermittent missing values will first be imputed using the Fully Conditional Specification method, which is appropriate for non-monotonic missing data for binary data.
- The monotone missing values will then be multiply imputed using the monotone logistic regression imputation method (Allison, 2005). A monotone missing pattern is such that in the event that a variable is missing it is implied that all subsequent variables are also missing (i.e. once a subject withdraws from study, no additional data is expected for that subject).
- For each stage, MI will be performed within treatment group with covariate adjustment the same as the primary analysis of the primary endpoint and non-missing outcomes for asthma worsening. Should convergence issues occur due to small cell size for the categorical covariates at either stage, they will be removed from the model.
- The primary analysis of the primary endpoint as described in Section 8.3.1 will be performed for each complete, imputed dataset.
- Fifty imputations will be performed.
- Results of the logistic regression on the multiple imputed data sets will be combined to generate an overall estimate and associated variance using Rubin's rules (Rubin, 1987).

The imputed data logistic regression model-based estimates of the proportion of subjects with asthma worsening, ORs, corresponding 95% CIs, and p-values will be reported. Percentage reductions and corresponding 95% CIs will also be provided.

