8.3.2.1. Change from Baseline to Week 24 Endpoints

Change from baseline to Week 24 in ACQ-5 score, pre-bronchodilator FEV₁, postbronchodilator FEV₁, and AM PEF will be analyzed as described below. The ACQ-5 is a five-item questionnaire which has been developed as a measure of the subject's asthma control that can be quickly and easily completed (Juniper E. F., 2005). The response options for each of these questions consists of a zero (no impairment/limitation) to 6 (total impairment/limitation) scale with the total score ranging from 0 to 30. ACQ-5 score is the average of the 5 non-missing items and will be calculated at each visit for each subject. The minimal clinically important difference (MCID) is 0.5 points.

For AM PEF, the baseline value is defined as the mean over the last 7 days of the Run-in including the value on Day 1 and Week 24 is defined as the mean over the last 7 days prior to Week 24 including the value on the day of the Week 24 visit. For the other endpoints, the baseline value is defined as the last non-missing value on or before the date of the first dose of study treatment.

If the number of subjects overall with a missing change from baseline value is < 5% for a particular endpoint:

- The primary analysis will be analysis of covariance (ANCOVA) without MI.
- As a sensitivity analysis, mixed-effects model with repeated measures (MMRM) without MI will also be performed.

If the number of subjects overall with a missing change from baseline value is \geq 5% for a particular endpoint:

- The primary analysis will be ANCOVA with MI.
- As sensitivity analyses, MMRM with MI, ANCOVA without MI, and MMRM without MI will also be performed.

Post-bronchodilator FEV_1 will not be analyzed using MMRM as it is collected at only one post-baseline timepoint.

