Each secondary endpoint of change from baseline to Week 24 will be analyzed using ANCOVA models. For this analysis, the MI procedure analogous to that described in Section 8.3.1.1.4 will be performed if the number of subjects overall with a missing change from baseline value is \geq 5% with the following modifications for cts data: (1) intermittent missing values will be imputed using the Markov Chain Monte Carlo (MCMC) method (Schafer, 1997), and (2) monotone missing values will be imputed using a regression model. Covariate adjustment will be the same as for the primary endpoint for ACQ-5 score and pre-bronchodilator FEV₁. For postbronchodilator FEV₁ and AM PEF, the covariates used in the model will be the same as for the primary endpoint except that baseline pre-bronchodilator FEV₁ will be replaced with baseline post-bronchodilator FEV₁ or baseline AM PEF, depending on the endpoint of interest. ANCOVA without MI will be performed similarly as described above without the imputation of values.

Descriptive statistics for change from baseline to Week 24 along with the LS means, SEs, and corresponding 95% CIs for each treatment group will be presented. Differences in LS means, SEs, corresponding 95% CIs, and p-values for each GB001 group versus placebo will also be constructed from the ANCOVA models.

In addition, each secondary endpoint of change from baseline to Week 24 will be analyzed by MMRM except for change from baseline to Week 24 in post-bronchodilator FEV₁. MMRM will

be performed using a restricted maximum-likelihood (REML)-based approach and an unstructured covariance structure to model within-subject error. The MMRM model will include change from baseline values up to Week 24 as the response variable; the fixed, categorical effects of treatment group, ICS dose (medium or high) at randomization, region, visit, and treatment group by visit interaction; and the cts, fixed covariates of baseline value and baseline value by visit interaction.

Parameters will be estimated using REML with the Newton-Raphson algorithm. Treatment comparisons will be derived from the MMRM. Differences in LS mean changes from baseline, the corresponding 95% CIs, and p-values with Kenward-Roger adjustment (Kenward, 1997) will be provided for comparison for each GB001 group versus placebo. LS means will be reported along with SEs and corresponding 95% CIs, and differences between treatment groups reported with LS means, SEs, corresponding 95% CIs, and p-values.

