Models used for the subgroup analyses will be the same as those used for the primary and secondary efficacy endpoints as specified in Section 8.3.1 and Section 8.3.2.1 with covariates for the subgroup (if different than the aforementioned covariates i.e. baseline ICS dose (medium or high) at randomization and region; for the efficacy-related baseline characteristic subgroups, baseline pre-bronchodilator FEV_1 or baseline ACQ-5 score will be replaced with a categorical subgroup variable) and treatment group by subgroup interaction added. If the model does not converge, a reduced model including only treatment group, ICS dose at randomization, and region will be used.

Heterogeneity of treatment effect across different levels of each subgroup will be evaluated by presenting p-values for the treatment by subgroup interaction. The interaction term tests whether the treatment effect is significantly different across different levels of the subgroup, between males and females, for example. If a subgroup variable has more than two levels then the least severe level (where applicable) will be used as the reference subgroup, and the test will assess whether the treatment effect in the more severe levels differs from that in the reference subgroup.

Forest plots of the treatment effect estimates and corresponding 95% CIs from the subgroup analyses will be provided.

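### Subgroup analyses of ACQ-5 and FEV1 add a treatment-by-subgroup interaction that the specified multiple imputation leaves out, a small and avoidable bias for most subgroups

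*SAP*

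**What the plan says.** SAP 8.4 plans subgroup analyses of the primary endpoint, ACQ-5 and pre-bronchodilator FEV1. It says that "Models used for the subgroup analyses will be the same as those used for the primary and secondary efficacy endpoints", with a term for the subgroup and "treatment group by subgroup interaction added". Heterogeneity is judged from interaction p-values and forest plots. Section 8.4 does not mention imputation.

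For the two continuous endpoints, SAP 8.3.2.1 sets the method by the amount of missing data:

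- Below 5% missing: "The primary analysis will be analysis of covariance (ANCOVA) without MI".
- At 5% or more: "The primary analysis will be ANCOVA with MI". In that case "the MI procedure analogous to that described in Section 8.3.1.1.4 will be performed", with two changes for continuous data: MCMC for intermittent gaps and regression for monotone gaps.

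The procedure referred to, in SAP 8.3.1.1.4, specifies that "MI will be performed within treatment group with covariate adjustment the same as the primary analysis of the primary endpoint", together with the non-missing outcomes. SAP 8.3.1 gives those covariates: "The model will include covariates for treatment group, ICS dose (medium or high) at randomization, region (North America, Eastern Europe, Western Europe". Two continuous measures complete the list, FEV1 before bronchodilator and the ACQ-5, each taken at baseline. Fifty imputations are planned.

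**The concern.** An imputation model should contain every variable whose relation to the outcome the analysis model will estimate. If it leaves one out, missing values at both levels of that variable are drawn from a common distribution within each arm, given the other predictors. The imputed subjects then show no subgroup difference beyond what their covariates and earlier visits carry, and they dilute or distort the difference seen in the observed subjects.

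The affected quantity is the one 8.4 uses to judge whether benefit differs between kinds of patient. Eosinophilic inflammation defines the target population (Protocol 4.2.1), and 8.4 lists several eosinophil and FeNO cut-points. Interaction tests are weak at this sample size, so an avoidable distortion is worth removing even if it is small.

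**Working it through.** **1. The plan's own figure.** The documents give no number for subgroup interactions or for the effect of imputation. The nearest is the 8% dropout in SAP 2.5, which can be reproduced:

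- Odds ratio = (0.102/0.898)/(0.25/0.75) = 0.341, the stated 66% reduction.
- Wald test on the log odds ratio: n = 7.849 × [1/(0.25×0.75) + 1/(0.102×0.898)] / (ln 0.341)² = 110.05 per arm.
- 110.05/0.92 = 119.6, about 120 per arm and 480 in total.

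So 8% is a real planning input and exceeds the 5% MI threshold. It was set for the binary primary endpoint and does not forecast missing Week 24 ACQ-5 or FEV1.

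**2. Which subgroups are exposed.** Comparing the 8.4 list with the imputation covariates:

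| Subgroup | In the imputation? |
|---|---|
| ICS dose at randomization, region | Yes; within-arm imputation preserves the interaction |
| Baseline ACQ-5 (<1.5, ≥1.5) | Largely, through continuous ACQ-5 |
| Actual ICS dose, percent predicted FEV1 | Probably partly, through randomized dose and baseline FEV1 (not simulated) |
| Age, sex, BMI, exacerbation history, eosinophils, FeNO, IgE, vitamin D, chloride | No |

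A simulation at 8% missing, without earlier visits, recovered 1.00 of the interaction for randomized ICS dose, 0.98 for baseline ACQ-5 and 0.93 for a subgroup outside the model.

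**3. Size when missingness is similar across arms and unrelated to the subgroup.** Let m be the missing fraction. With no help from earlier visits, a within-arm subgroup difference is multiplied by a = 1 − m, because imputed subjects contribute no difference. The interaction shrinks by the same factor; at m = 0.08, a = 0.92.

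Earlier visits recover part of this, because they carry some of the subgroup effect. A large-sample, two-arm simulation gave these ratios of estimated to full-data interaction. Its assumptions, which are not in the documents, were a 50% subgroup, a 0.4 SD interaction, seven post-baseline visits and within-subject correlation of 0.5–0.7.

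| Missing | No earlier visits | With earlier visits |
|---|---|---|
| 5% | 0.95 | 0.96–0.99 |
| 8% | 0.92 | 0.94–0.98 |
| 15% | 0.84 | 0.89–0.97 |
| 20% | 0.81 | 0.85–0.95 |

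The lower ends arise when the effect builds up over visits, so that early values carry less of it. A further two-arm simulation gave 0.94–0.99 at 8%. With the subgroup in the imputation at 8% missing, the ratio was 0.998 (Monte Carlo SE 0.002).

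**4. Size against sampling error.** For two arms of 120 with a 50% subgroup there are four cells of 60, so the interaction SE is √(4/60) = 0.258 SD. The upper-end loss is 0.08 × 0.4 = 0.032 SD, and 0.032/0.258 = 0.12 SE. Power is Φ(0.4/0.258 − 1.96) = 34% without shrinkage and Φ(0.368/0.258 − 1.96) = 30% with it.

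**5. Direction.** Let a₁ and a₀ be the retention factors in the active and placebo arms, s the placebo-arm subgroup effect and d the interaction. The estimate tends to a₁(s + d) − a₀s = a₁d + (a₁ − a₀)s. The second term vanishes only if retention is equal or the subgroup is not prognostic. As an illustration with no earlier visits, take s = d = 0.4:

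- 5% missing on active, 15% on placebo: 0.95×0.4 + 0.10×0.4 = 0.42, or 105% of d.
- 15% on active, 5% on placebo: 0.85×0.4 − 0.10×0.4 = 0.30, or 75% of d.

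**The case against.** **Reuse is not stated.** A reader might infer that the SAP orders the main-analysis imputations to be reused for subgroups. It does not; 8.4 is silent. Since 8.3.1.1.4 ties the imputation covariates to the analysis covariates, a programmer could reasonably carry the subgroup through. This stands as a limit on the claim. Still, 8.3.1.1.4 points to the covariates of the primary analysis, and neither modification in 8.3.2.1 adds a subgroup, so following the text literally omits it.

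**MI may not be used.** Below 5% missing there is none, and subjects who stop treatment are encouraged to keep attending (Protocol 7.1). This also stands. MI is likely, not certain. FEV1 is the more exposed endpoint, because Protocol Appendix 12 allows questionnaires at home but names no home alternative for spirometry.

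**The effect is negligible.** At 8% missing it is a small fraction of a standard error, in analyses that are unpowered and not adjusted for multiplicity. That is correct and sets the severity. A reader might take the larger losses at 15% or 20% as what the SAP expects from the pandemic. SAP 3.3 says instead that the degree of impact is not known and lists only potential effects.

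**Evidence on who benefits does not rest on these endpoints alone.** The primary analysis of the primary endpoint and the exacerbation-rate analysis use no MI, and both have eosinophil and FeNO subgroup analyses. This stands.

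**Conclusion.** The point holds as a minor gap in specification. If at least 5% of Week 24 changes are missing and the text is followed as written, the treatment-by-subgroup interaction for ACQ-5 and pre-bronchodilator FEV1 is biased for subgroups not covered by the imputation covariates. With similar missingness across arms, unrelated to the subgroup, the loss is at most about the missing fraction: roughly 1–8% at 8% missing, worth no more than about 0.12 SE if the true interaction is 0.4 SD.

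Two stronger readings are not supported. The bias is not always toward no heterogeneity: unequal missingness with a prognostic subgroup can inflate or deflate the estimate. Nor are all subgroups affected: randomized ICS dose and region are preserved, and baseline ACQ-5 nearly so. The visit correlations, subgroup prevalence, interaction size and missingness patterns used here are assumptions. Conclusions on the primary endpoint are untouched.

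**What to change.** Add one sentence to SAP 8.4: when MI is used for an ACQ-5 or pre-bronchodilator FEV1 subgroup analysis, the within-arm imputation is re-run with that subgroup variable added as a predictor, one subgroup definition at a time. Because imputation is done separately by arm, the main effect of the subgroup in each arm's model is enough to preserve the interaction.

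A single imputation model holding every subgroup variable is not advisable. With about 120 subjects per arm and several overlapping cut-points it would be overloaded, and 8.3.1.1.4 already foresees dropping categorical covariates when cells are small.

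The cost is some programming, an extra run of 50 imputations per subgroup definition, and a stated rule for subjects whose subgroup variable is itself missing; FeNO is an example, since Protocol 8.6.2 makes its measurement optional. No new data are needed.

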6.4. Efficacy-Related Baseline Characteristics

Efficacy-related baseline characteristics will be summarized for the ITT and per protocol populations for the following parameters:

- Pre-bronchodilator FEV₁ at Screening and Baseline (L; cts)
- Post-bronchodilator FEV₁ at Screening (L; cts)
- Pre-bronchodilator percent predicted FEV₁ at Screening (%; cts; $< 60, \ge 60$)
- Post-bronchodilator percent predicted FEV₁ at Screening (%; cts)
- Pre-bronchodilator FEV₁/forced vital capacity (FVC) at Screening and Baseline (ratio; cts; < 0.7, ≥ 0.7)
- FEV₁ reversibility at Screening (%; cts)
- AM PEF over last 7 days of the Run-in (L/min; cts)
- Rescue medication usage over last 7 days of the Run-in (puffs/day; cts)
- ACQ-5 score at Baseline (cts; $< 1.5, \ge 1.5$)

Efficacy-related baseline characteristics will also be presented in a by-subject data listing.

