8.4. Examination of Subgroups

Subgroup analyses of the primary and two secondary (ACQ-5 score and pre-bronchodilator FEV₁) efficacy endpoints will be performed for all of the subgroups specified below. In addition, subgroup analyses of the secondary efficacy endpoint of annualized rate of severe asthma exacerbations will also be performed for select subgroups as specified below. For any subgroup level that does not comprise $\geq 10\%$ of the ITT population, the analyses based on the models will not be performed. The subgroups of interest are described below.

Demographic and general baseline characteristic subgroups:

- Age (years; $< 65, \ge 65$)
- Sex (male, female)
- BMI (kg/m²; < 30, \geq 30)
- Baseline ICS dose ([per randomization and per actual value]; medium, high, including comparison of GB001 medium to Placebo high)
- Region (North America, Eastern Europe, Western Europe)
- Total number of exacerbations in the past 12 months (1, > 1)

Efficacy-related baseline characteristic subgroups:

- Pre-bronchodilator percent predicted FEV₁ at Screening (%; $< 60, \ge 60$)
- ACQ-5 score at Baseline ($< 1.5, \ge 1.5$)

Biomarker baseline characteristic subgroups:

- Blood eosinophils at Baseline (GI/L; < 0.20, ≥ 0.20; < 0.25, ≥ 0.25 [including for annualized rate of severe asthma exacerbations]; < 0.30, ≥ 0.30)
- FeNO at Baseline (ppb; < 25, ≥ 25 [including for annualized rate of severe asthma exacerbations]; < 30, ≥ 30; < 35, ≥ 35; < 50, ≥ 50)
- Blood eosinophils and FeNO at Baseline ([blood eosinophils < 0.25 GI/L and FeNO < 25 FeNO ppb] vs [blood eosinophils ≥ 0.25 GI/L and/or FeNO ≥ 25 ppb] {including for annualized rate of severe asthma exacerbations}; repeat for 0.25 vs 30, 0.25 vs 35, and 0.25 vs 50)
- Blood eosinophils and FeNO at Baseline ([blood eosinophils < 0.25 GI/L and FeNO < 25 FeNO ppb] vs [blood eosinophils < 0.25 GI/L and FeNO ≥ 25 ppb] vs [blood eosinophils ≥ 0.25 GI/L and FeNO < 25 ppb] vs [blood eosinophils ≥ 0.25 GI/L and FeNO < 25 ppb] vs [blood eosinophils ≥ 0.25 GI/L and FeNO < 25 ppb] vs [blood eosinophils ≥ 0.25 GI/L and FeNO > 25 ppb]; including for annualized rate of severe asthma exacerbations)
- IgE (IU/mL; normal [≤ 158], high [> 158])
- 25-Hydroxyvitamin D at Baseline $(ng/mL; \leq 20, > 20)$
- Chloride at Baseline (mmol/L; ≤ Quartile 1, > Quartile 1-≤ Quartile 2, > Quartile 3-≤ Quartile 3, > Quartile 3, where quartiles are based on the ITT population)

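### SAP 8.4 replaces the continuous baseline with a two-level category in the FEV1 and ACQ-5 severity subgroup models, at a small cost in precision in two of six models

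*SAP*

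**What the plan says.** The main logistic model (SAP 8.3.1) adjusts for treatment, ICS dose at randomization, region, "baseline pre-bronchodilator FEV₁, and baseline ACQ-5 score". For the ANCOVA of change to Week 24, SAP 8.3.2.1 says "Covariate adjustment will be the same as for the primary endpoint for ACQ-5 score" and for pre-bronchodilator FEV1, so both of those models also carry the two continuous baselines.

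SAP 8.4 applies these models to subgroups for three endpoints: the primary endpoint, ACQ-5 change and pre-bronchodilator FEV1 change. In general it adds the subgroup term and a treatment-by-subgroup interaction and leaves the other covariates in place. It then makes an exception "for the efficacy-related baseline characteristic subgroups": the continuous FEV1 or ACQ-5 baseline "will be replaced with a categorical subgroup variable".

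There are two such factors, each with two levels: "Pre-bronchodilator percent predicted FEV₁ at Screening", cut at 60%, and "ACQ-5 score at Baseline", cut at 1.5. The FEV1 covariate being removed is on another scale. SAP 6.4 lists it as "Pre-bronchodilator FEV₁ at Screening and Baseline (L; cts", that is, continuous and in litres. Results are reported as interaction p-values and forest plots.

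**The concern.** A two-level category carries less information than the measurement it is cut from. In a change-from-baseline ANCOVA the outcome's own baseline is usually the strongest covariate, so coarsening it leaves baseline variation in the residual and widens the intervals.

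Elsewhere the SAP avoids this. Its other change-from-baseline ANCOVAs (AM PEF, AQLQ-S, SNOT-22, the diary endpoints, FeNO, and sputum cells on the log scale) all adjust for the outcome's own continuous baseline.

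For FEV1 the replacement is not even a coarser version of the same variable. It is taken at Screening rather than Visit 2, and it is scaled to each subject's predicted normal. Subjects with quite different litres can therefore share a level.

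At stake are the width of the severity rows in the forest plots for the two continuous endpoints and, for the primary endpoint, whether those rows show the same conditional odds ratio as the rest.

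**Working it through.** **The plan's own figure.** The SAP gives no precision or power figure for any subgroup model. Its one design figure is 80% power for each dose (SAP 2.5). With 120 × 0.92 ≈ 110 per arm and rates of 25% and 10.2%, the log odds ratio is 1.077 and its SE is √(1/20.63 + 1/10.08) = 0.384. Power is then Φ(1.077/0.384 − 1.96) = 79.98%. The figure reproduces but does not bear on this point.

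**Which models are affected.** Two factors times three endpoints gives six models. I read the *or* in SAP 8.4 as replacing only the matching covariate. ACQ-5 change in the FEV1 subgroup then keeps baseline ACQ-5, and FEV1 change in the ACQ-5 subgroup keeps baseline FEV1. An outcome loses its own continuous baseline in two of the six. In two others only the other measure's baseline is replaced. The remaining two are logistic models for the primary endpoint.

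**Formulas for the two ANCOVA models.** Assume a normal baseline and equal SDs at baseline and Week 24, and ignore the remaining covariates. Let ρ be the baseline-to-Week-24 correlation, c the share of subjects in one level, z the normal cut-point, and r the correlation between the categorised variable and the removed covariate.

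- Share of the categorised variable's variance kept by the split: f = φ(z)²/[c(1−c)]. At a median split, 0.1592/0.25 = 0.637. At 20/80, 0.0784/0.16 = 0.490.
- Baseline variance left unadjusted: w = 1 − r²f.
- Residual variance of change, category only against continuous baseline: V = [(1−ρ)²w + 1 − ρ²]/(1 − ρ²). The SE ratio is √V.

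**ACQ-5 change in the ACQ-5 subgroup** (r = 1, so w = 0.363 at a median split and 0.510 at 20/80). For example, at ρ = 0.5 and a median split, V = (0.25 × 0.363 + 0.75)/0.75 = 1.121.

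| Assumed ρ | Median split: V, SE | 20/80 split: V, SE |
|---|---|---|
| 0.5 | 1.12, +6% | 1.17, +8% |
| 0.6 | 1.09, +4% | 1.13, +6% |
| 0.8 | 1.04, +2% | 1.06, +3% |

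A variance ratio of 1.121 corresponds to losing 1 − 1/1.121 ≈ 11% of the sample for that contrast.

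**FEV1 change in the FEV1 subgroup.** Assume r between 0.6 and 0.8 for Screening percent predicted against baseline litres.

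- Smallest loss (r = 0.8, median split): w = 1 − 0.64 × 0.637 = 0.593. The SE ratio is 1.051 at ρ = 0.7 and 1.024 at ρ = 0.85.
- Largest loss (r = 0.6, 20/80 split): w = 1 − 0.36 × 0.490 = 0.824. The SE ratio is 1.070 at ρ = 0.7 and 1.033 at ρ = 0.85.

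**Simulation check of the ANCOVA result** (four arms of 110, 600 runs per setting). At ρ = 0.5 the reported interaction SE rose by a factor of 1.057 (median split) and 1.080 (20/80), matching the formula. The run-to-run spread of the estimate rose by 1.053 and 1.054. At 20/80 the true loss is thus below the reported one, because the pooled residual variance overstates the variance in the smaller level. For the extreme 20% of a normal variable, λ = 0.280/0.20 = 1.400, and the within-level variance is 1 + 0.842 × 1.400 − 1.400² = 0.22, against 0.51 pooled. In every setting the mean interaction estimate was close to zero with either covariate set, with differences of at most 0.009.

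**Primary logistic endpoint.** This was simulated with a 50:50 split, a placebo rate of about 25%, a treatment odds ratio of 0.34 and no true interaction. The interaction SE without the continuous covariate was 0.998 to 0.989 times that with it, as the covariate's odds ratio per SD went from 1.0 to 2.0. Between 2% and 11% of 1,500 runs per setting were dropped for non-convergence or an SE above 5.

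**The case against.** The strongest reply is that this is an efficiency preference, not an error. The swap is prespecified and openly stated. It touches two subgroup factors, reported without multiplicity control and with no stated subgroup power, and a CI a few percent wider is unlikely to change how a forest plot is read. A motive is also easy to imagine: one coding of a measure per model, in a four-arm interaction model for which SAP 8.4 already plans a non-convergence fallback. All of this stands as to importance. As a reason it is only partial. A category and its continuous source are not perfectly collinear and can be fitted together, and for FEV1 the two are different variables.

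The documents do not support several stronger inferences that a reader might draw:

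- *Regression to the mean biases the subgroup effects.* Within a level defined at baseline it is expected equally in all arms. Randomization leaves only chance imbalance, which is the precision loss already counted.
- *All severity-subgroup intervals widen.* The primary endpoint's interaction SE does not grow.
- *Most of the baseline adjustment is lost.* For ACQ-5 the split removes about 36% (median) to 51% (20/80). The description fits only FEV1, where under the assumed correlations 18% to 41% is kept.
- *The results cannot be compared with other subgroup rows.* A linear-model treatment difference targets the same quantity under either covariate set. Only the logistic odds ratio changes what it conditions on.
- *There is no reason for the swap.* The SAP states none, which is a weaker statement.

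**Conclusion.** The point holds, and it is minor. In two of six subgroup-by-endpoint models the outcome loses its own continuous baseline, and precision is given up that the trial has already collected the data to keep. The reported SE is about 2-6% larger for ACQ-5 change at a median split and 3-8% larger at 20/80 (ρ from 0.5 to 0.8). For FEV1 change it is about 2-7% larger (ρ from 0.7 to 0.85, r from 0.6 to 0.8, splits from 20/80 to even). For the primary endpoint nothing is lost in precision, but the severity rows would show odds ratios conditional on a different covariate set from the other rows.

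The values of ρ and r, the split shares and normality are assumptions, because the documents give none of them. The count of two models rests on reading the clause as replacing only the matching covariate. The main primary and secondary analyses keep both continuous baselines and are unaffected.

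**What to change.** In SAP 8.4, replace the substitution clause with wording such as: *For the percent-predicted FEV1 and ACQ-5 subgroups, the continuous baseline covariates are kept, and the categorical subgroup term and its interaction with treatment are added.*

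This puts every forest-plot row on the same baseline adjustment. The existing non-convergence fallback can stay as it is. The cost is one clause in the SAP and one degree of freedom per model, with no new data.
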